8.3 Patient safety and wellbeing during qualitative interviews

There is potential that some participants may feel upset during the interview as a result of talking about their life circumstances and the effect COPD and its treatment has on them. However, this is not more than would be expected in any clinical encounter. Participants will be listened to sensitively, allowed breaks or to withdraw from the interview, if they wish. It will not be the Qualitative Researcher's role to offer any counselling to participants, but if their distress persists, with their permission, the Qualitative Researcher would pass their concerns on to their usual care team or recommend that the participant contacts their usual care team or GP for a review. Participants may find some benefit from taking part in an interview as they will be given time to speak about their situation, an opportunity that some may find helpful.

8.4 Qualitative Data Analysis

Interview transcripts will be pseudo-anonymised, and transcripts will be imported into NVivo, a qualitative data management software. The analysis of the qualitative interview data will be conducted using a matrix-based approach to qualitative data analysis. The TFA constructs will be used as a thematic framework for initial deductive coding and exploration of data, followed by inductive coding and development of themes where appropriate (including existing concepts such as 'safety objects' that are relevant to the hand-held fan). The analytic process will progress from classification of data to synthesis of themes that explain acceptability in relation to the seven

constructs of the TFA, and which can be mapped back to each of the seven key uncertainties as outlined in section 8.2.6.

9. SAFETY ASSESSMENTS/ADVERSE EVENTS

The adverse event (AE) reporting period for this trial begins at screening and ends at the participant's final study visit. Each trial participant will be questioned about adverse events at each visit. The investigator will record all directly observed AEs and all AEs spontaneously reported by the trial participant. A pre-existing condition (i.e. a disorder present before the AE reporting period started, and noted on the pre-study medical notes), is not to be reported as an AE unless the condition worsens or episodes increase in frequency during the AE-reporting period. All AEs (serious and non-serious) will be recorded in patients' data collection forms (eCRFs) using the AE report form. All adverse events will be recorded in patients' medical records, and followed-up until the event has resolved, or a decision has been taken to discontinue follow-up.

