1. BACKGROUND AND RATIONALE

Over-reliance on short-acting beta agonist inhalers (SABA) in COPD can reflect uncontrolled breathlessness, can cause side effects (tremor/palpitations), and is harmful to the environment. We will conduct a feasibility randomised controlled trial (RCT) of a simple and scalable breathlessness management intervention in COPD patients who over-use SABA to investigate i) the feasibility and optimal design of a definitive trial investigating the potential to improve symptom control and reduce SABA reliance in COPD, and ii) explore factors impacting wide-scale adoption of our intervention across the NHS.

SABA are the most prescribed inhalers in England. They relax airway smooth muscle, temporarily relieving symptoms caused by airway narrowing (bronchospasm). However, SABA over-use is linked with poor patient outcomes and environmental damage.

High SABA use is well delineated in asthma where it is associated with exacerbation risk, health-careresource utilisation and excess mortality^{1,2}. Although less studied, high SABA use in COPD is associated with worse quality-of-life and exacerbation risk^{3,4,5}; events that drive disease progression and mortality⁶⁻⁸. Where policy and guidelines are helping drive down SABA use in asthma, less is known about how to achieve this in COPD.

COPD typically affects older adults and is associated with deprivation. Breathlessness is common in COPD⁹, impairs quality-of-life¹⁰, physical and social function¹¹, and leads to dependence on health services^{12,13}. Breathlessness causes vicious cycles of activity avoidance, deconditioning, and anxiety-panic, worsening breathlessness¹⁴. Optimal symptom and disease-control is therefore crucial in COPD. However, despite availability of evidence-based, non-pharmacological breathlessness interventions such as the hand-held fan (HHF)^{15,16}, pharmacological strategies such as SABA are often prioritised, risking over-use and over-reliance.

SABA's role in managing daily variations in chronic breathlessness in COPD is poorly understood⁴ with people with COPD typically already established on long-acting bronchodilators¹⁷. Managing major symptom components with the HHF and addressing unhelpful breathing patterns and anxiety, may be more effective than, and reduce, SABA use.

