3. STUDY DESIGN

Multicentre, parallel-group, open-label, randomised controlled, hybrid Type-I effectivenessimplementation feasibility study. Patients will be randomised to either usual care or the FanFIRST intervention in a 1:1 ratio using random permuted blocks. Randomisation will be stratified by site and based on self-reported HHF usage (any reported HHF-use) within the past month.

Taking an overall effectiveness research perspective, consistent with the MRC's updated framework for developing and evaluating complex interventions²²²², the study incorporates a theory-based approach to assess how processes, impact mechanisms and contextual factors shape outcomes²³²³²³.

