4. STUDY POPULATION

Eighty eligible consenting people with COPD and high SABA-use[^] during the year prior to study recruitment. Participants that do not meet all of the eligibility criteria will not qualify for enrolment. A study screening and enrolment log will be kept to include all potential participants sent a participant information sheet, recording reasons for ineligibility when applicable. All consenting participants will be provided with an automatically generated subject identification number (SIN) and enter study screening. For participants that do not pass screening, reasons for failure will be recorded on the screening log and within REDCap.

[^]For this study, high SABA-use will be defined as 12 or more SABA prescriptions issued during the prior 12-months with self-reported SABA-use most days.

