| cause of their breathessnessynigh SADA use: | Questionnaire* | the Propeller sensors to apply to |
| SFP4: Has a COPD exacerbation requiring oral corticosteroids and/or antibiotics and/or | | their prescribed SABA inhalers. |
| hospitalisation occurred within 4-weeks before recruitment (taken from last day of | | Training on their usage will be |
| exacerbation treatment). Record number of COPD exacerbations for the last 12 | | provided onsite, with written |
| months, including dates, treatments received, and whether ED attendance and/or | | instructions to also be provided. |
| hospitalisation occurred | | Participants who will not be using |
| | | the app will have their sensor |
| SFP5a: Does participant self-report <daily saba="" td="" use?<="">	synced onsite through a site specific	</daily> | | synced onsite through a site specific |
| | | app. |
| SFP5b:Have they had <12 SABA inhalers/canisters prescribed within the past year. | | app. |
| Record Name, dose and number of prescriptions within the past 12-months for all | | Provide a 'Study SABA Information |
| | | Card'(SAIC) if the participant's |

| Medical History ⁺ | Questionnaires | Medical tests/Equipment |
|---|----------------|----------------------------------|
| | | provision |
| inhaled medications. Note the current SABA prescription and confirm that it is a | | SABA is prescribed using the |
| pressurised metered dose inhaler (pMDI). | | generic drug name rather than by |
| SFP6: Have they been receiving optimal guideline recommended inhaled treatment for COPD^? | | brand. |
| Smoking status. SFP7 : <10 pack per year smoking history (see questionnaire section for SFP8) . | | |
| History of HHF use: | | |
| Question 1: 'Have you used the HHF in the past month – Yes/No. If 'Yes' is ticked, | | |
| follow up question 'How often 1) Every day, 2) Most days, 3) Occasionally or rarely | | |
| Record of Health Care Resource Use in the past 4-weeks. See section 7.4.3 for details of this | | |

^Optimal treatment is defined as a minimum of dual-acting bronchodilator therapy (long-acting beta-agonist and long-acting muscarinic antagonist) with or without an inhaled corticosteroid.

[†]In addition, to the information collected in Table 4, the following demographic information will be collected: age, gender, ethnicity, socioeconomic status [obtained from postcode], educational attainment

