9.4 Expected Serious Adverse Events

Due to the seriousness of the disease in this study, the expected SAEs detailed below will not require reporting within 24hrs on the initial and follow-up SAE forms, but will still need to be reported on the trial's AE report form.

Expected serious adverse events in this study include:

- hospital admission due to COPD exacerbation
- admission to hospital or prolongation of existing hospitalisation for a pre-existing condition; and
- elective surgery.

All serious events that do not require reporting within 24hrs will still require reporting within 14 days of the researcher becoming aware of the event.

10.DATA HANDLING AND QUALITY ASSURANCE

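### Section 9 does not settle whether a non-hospitalised COPD exacerbation is an adverse event, so AE-form counts of these episodes rest on the discretion of unblinded investigators

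*Protocol*

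**What the plan says.** Section 9 runs the AE period from screening to the final visit. A disorder present before that period "is not to be reported as an AE unless the condition worsens or episodes increase in frequency during the AE-reporting period". The rule gives no criterion for worsening, no reference rate and no comparison window.

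The same section says that participants are asked about adverse events at every visit, and then describes what is written down: "The investigator will record all directly observed AEs and all AEs spontaneously reported by the trial participant".

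Section 9.3 classes COPD-related admissions as expected SAEs. Section 9.4 lists admission for a COPD exacerbation among the expected SAEs, and also "admission to hospital or prolongation of existing hospitalisation for a pre-existing condition; and" elective surgery. These must still go on the AE report form and be reported within 14 days.

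Section 4.2 contains a working definition of an exacerbation, based on need for oral corticosteroids, antibiotics or hospitalisation. It is used only for exclusion and for screen-fail point 4. At screening, Table 4 asks sites to "Record number of COPD exacerbations for the last 12" months, with dates and treatments. Section 6.2 lists no exacerbation outcome during follow-up.

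The design is "Multicentre, parallel-group, open-label, randomised controlled". Section 11 plans descriptive safety summaries and no formal tests.

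**The concern.** COPD is episodic and everyone enrolled has it, so the pre-existing-condition rule governs a common and foreseeable respiratory event. Two investigators can look at the same course of steroids or antibiotics and, in good faith, reach opposite answers. One sees the condition worsening and records an AE. The other sees the patient's usual pattern and records nothing. After Day 0 both know the allocation.

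The event matters to this programme. The Background says that "high SABA use in COPD is associated with worse quality-of-life and exacerbation risk", describes such events as drivers of progression and mortality, and names safety among the things the definitive trial will evaluate. Table 2 includes use of the fan in place of a SABA inhaler in the rationale. Whether exacerbations rise or fall, the next trial needs a count made the same way in both arms. A later analysis plan cannot restore AE entries that sites were entitled not to make.

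**Working it through.** The protocol states no figure on this point, so there is none to reproduce. The check is textual, with illustrative arithmetic.

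**Inputs from the protocol.** "Eighty eligible consenting people with COPD" (Section 4), allocated "in a 1:1 ratio using random permuted blocks" (Section 3), so about 40 per arm. The AE window runs from Day -28 to Day 84, about 28 + 84 = 112 days. Follow-up after randomisation is 84 days. No exacerbation rate is given. I assume 0.5 to 4 per patient-year for illustration only.

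**Step 1: can the frequency limb be applied?** History covers 12 months and the AE window covers 112 days. One episode annualises to 365/112 = 3.26 per year over the AE window, or 365/84 = 4.35 per year over the post-randomisation period.
- Comparing rates over the AE window, one episode is an increase for a patient with 3 or fewer in the prior year and not for one with 4 or more.
- Comparing raw counts, one episode is an increase only for a patient with none in the prior year.

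The two readings disagree for every patient with 1, 2 or 3 prior episodes, and the protocol does not choose between them.

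**Step 2: does the worsening limb settle it?** The limbs are alternatives, so a site that treats any exacerbation as worsening records them all. Nothing requires that reading, and a site that reads worsening as a lasting change in the underlying disease falls back on Step 1.

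**Step 3: how many episodes could be involved?** Expected episodes per arm = 40 × rate × 84/365. P(at least one) = 1 − exp(−rate × 84/365), assuming Poisson counts.

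| Assumed rate per year | P(at least one in 84 days) | Expected episodes per arm |
|---|---|---|
| 0.5 | 11% | 4.6 |
| 1 | 21% | 9.2 |
| 2 | 37% | 18.4 |
| 3 | 50% | 27.6 |
| 4 | 60% | 36.8 |

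These are all exacerbations. Only the non-hospitalised share is open to discretion, and the protocol does not give that share, so the table is an upper bound.

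**Step 4: what can discretion do to the comparison?** With equal true risk p and recorded fractions s1 and s0, the apparent difference is p × (s1 − s0).
- 80% against 60% recorded: 0.20 × 0.20 = 4 points at p = 20%, and 0.40 × 0.20 = 8 points at p = 40%.
- 100% against 50% recorded: 0.20 × 0.50 = 10 points at p = 20%, and 0.40 × 0.50 = 20 points at p = 40%.
- 70% recorded in both arms: no false difference, but the event rate is understated. At 2 per year, 18.4 × 0.7 = 12.9 episodes per arm would be seen.

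**Step 5: what precision is available with complete recording?** The 95% half-width for a risk difference is 1.96 × √(2p(1 − p)/40). This gives about 13 points at p = 10%, 18 at 20%, 20 at 30% and 21 at 40%.

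**Step 6: neighbouring text.** Section 9.1 defines an AE broadly enough to include any exacerbation. Section 9 could make an admission for an unchanged pre-existing condition not an AE, while Section 9.4 requires the same admission to be reported. Section 9 has participants questioned, yet its recording sentence names only observed and spontaneously reported events.

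**The case against.** The case against is substantial, and much of it stands.

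- **Serious exacerbations are covered.** Sections 9.3 and 9.4 fix COPD admissions as expected SAEs that must be reported. This stands, and it confines the point to episodes managed outside hospital.
- **Other data exist in both arms.** The Table 1 footnote and Section 7.4.5 record new treatments, treatment changes and usual care received. Section 7.4.4 takes healthcare contacts from self-report and the electronic record. A reader might infer that exacerbations cannot be compared between arms at all, and these data show that this goes too far. However, the protocol states no derivation of exacerbations from them, the footnote does not name steroid or antibiotic courses, and a contact is not a diagnosis.
- **The two limbs are alternatives.** A reader might infer that frequent exacerbators are necessarily the ones omitted. That follows only if the frequency limb is applied alone on a rate basis. The rule is ambiguous and does not exclude them outright.
- **The protocol names no key harm.** A reader might infer that exacerbation is the most relevant harm of the fan. The Background ties exacerbation risk to high SABA use, and does not present it as a consequence of the fan.
- **Elicited events are probably recorded anyway.** Section 9 also says that all AEs are recorded, and nothing tells sites to discard elicited ones. The recording sentence is loose wording and a secondary point.
- **Sections 9 and 9.4 can be read together.** The specific SAE provisions may be taken to govern the general rule. That is reasonable, but the text does not say so.
- **The trial is small and descriptive.** Even complete recording leaves half-widths of about 13 to 21 points at assumed risks of 10-40%. This limits what any comparison could show, but it does not justify a count that depends on who made it.

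**Conclusion.** The point holds in a limited form. Section 9 leaves the recording of non-hospitalised COPD exacerbations to investigator discretion, and after Day 0 that discretion is exercised by unblinded staff. AE-form counts of these episodes are therefore not a reliable basis for comparing arms or for giving the definitive trial an event rate.

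The size cannot be fixed from the protocol. Under assumed risks of 20-40%, unequal recording could produce a false difference of 4-8 points (80% against 60%) or 10-20 points (100% against 50%). Equal under-recording would produce no false difference when true risks are equal, but would understate the rate. The protocol does not show that recording will in fact differ by arm. It only leaves room for that.

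The feasibility outcomes and traffic-light criteria are unaffected. The change is worth making because the recording rule belongs to the protocol and must be in place before sites start completing forms.

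**What to change.** In Section 9, exempt COPD exacerbations from the pre-existing-condition rule. Record every exacerbation that meets the Section 4.2 definition, from consent to Day 84, with start and stop dates, in both arms and regardless of prior frequency. Summarise post-randomisation episodes and participants affected by arm, descriptively.

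Amend the recording sentence so that it also covers AEs elicited by the questioning at each visit. Reconcile Section 9 with Section 9.4 on admissions for pre-existing conditions and on elective surgery, so that one event cannot be both outside the AE definition and a reportable SAE.

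The cost is protocol wording and one eCRF field. Treatment changes and healthcare contacts are already asked about from Day 0 onwards, so little is added to the visits. The downside is a longer AE listing. The change removes the discretion over what is recorded but does not improve precision, which remains limited by about 40 participants per arm.

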9.1 Definitions

AE (Adverse event): An adverse event is any untoward medical occurrence in a participant to whom a research intervention or procedure has been administered, including occurrences which are not necessarily caused by or related to that intervention or procedure.

Serious adverse event (SAE):

In research other than CTIMPs, a *serious adverse event* (SAE) is defined as an untoward occurrence that:

- a) results in death;
- b) is life-threatening;
- requires hospitalisation or prolongation of existing hospitalisation;
- d) results in persistent or significant disability or incapacity;
- e) consists of a congenital anomaly or birth defect; or
- f) is otherwise considered medically significant by the investigator.

9.2 Relationship to the Study Intervention

The investigator must make an assessment of the relationship of each event to the study intervention and classify it as either:

- unrelated e.g., where the event is definitely not; or unlikely to be; related to the intervention or a research procedure, **OR**
- related e.g., where the event is likely to be related to the intervention.

Additionally, the investigator must assess whether the AE is unexpected i.e., not listed in the study protocol as an expected occurrence.

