9.3 Serious Adverse Events

The investigator is required to determine if each adverse event is an SAE, as defined in section 9.1. Any SAE that is related to the study and unexpected must be reported to the Sponsor within 24 hours of research staff knowledge of the SAE. For SAE's, the following information will be collected:

- Full details in medical terms and case description
- Event duration
- Action taken
- Outcome
- Seriousness criteria
- Causality i.e., if event is related or unrelated to the intervention

Hospital admissions are common in this patient group due to their underlying disease. Thus, admissions related to their COPD, or co-morbidities, will be classified as an expected SAE. In expected SAE cases, the report will not have to be submitted within the timeframe of 24 hours as is expected in related or unexpected SAEs, but can be submitted for CI review within 14 calendar days.

Unexpected SAE's related to the intervention will be reported to the Research Ethics Committee that gave a favourable opinion of the study and the sponsor (Hull University Teaching Hospitals NHS Trust R&D department) **within 15 days** of the chief investigator becoming aware of the event using the Non-CTIMP safety report form available from: https://www.hra.nhs.uk/approvals-amendments/managing-your-approval/safety-reporting/

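### The two causality classes in section 9.2 are not complementary, and the REC trigger in 9.3 omits events caused by a research procedure

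*Protocol*

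**What the plan says.** Section 9.2 sets a two-way choice: "The investigator must make an assessment of the relationship of each event to the study intervention and classify it as either" one of two classes. The first is "unrelated e.g., where the event is definitely not; or unlikely to be; related to the intervention or a research procedure". The second, *related*, is also introduced by 'e.g.' and described as "where the event is likely to be related to the intervention". No other class or description is given.

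Section 9.3 builds the reporting rules on that choice and uses four different wordings:

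- 24-hour sponsor report: "Any SAE that is related to the study and unexpected must be reported to the Sponsor within 24 hours" of research staff learning of it.
- 24-hour sponsor report, mentioned again later in the section when expected SAEs are exempted: "as is expected in related or unexpected SAEs".
- Causality item collected for each SAE: "Causality i.e., if event is related or unrelated to the intervention".
- REC report within 15 days of the chief investigator becoming aware: unexpected SAEs related to the intervention.

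Section 9.4 adds a fallback: serious events outside the 24-hour rule are still reported within 14 days. Section 9.1 defines an adverse event by reference to a research intervention or a procedure, and section 9 starts adverse event reporting at screening.

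**The concern.** A two-level causality scale is acceptable, but its levels should cover every event between them and refer to the same causes. Here one level names two causes and the other names one. One level stops at unlikely and the other starts at likely. The classification matters because it decides whether an unexpected SAE goes to the REC and, under one of the two wordings, whether it goes to the sponsor within 24 hours.

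The omission of procedures is more than a drafting detail in this design. Before Day 0 no participant has received the study intervention, and the usual-care arm does not receive it until the end of the final visit (section 5.2). In those periods, study procedures such as spirometry and inhaler-sensor monitoring are the only study exposure that could cause an event.

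**Working it through.** The point concerns wording, so the check compares the descriptions and then follows example events through the rules. The Protocol gives no figure to reproduce.

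**Step 1. The two classes in 9.2.**

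| | Unrelated | Related |
|---|---|---|
| Strength of relation | definitely not, or unlikely | likely |
| Causes named | intervention or research procedure | intervention only |

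A relation judged possible (neither unlikely nor likely) matches neither description. An event likely caused by a procedure is ruled out of *unrelated* and is not described under *related*.

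**Step 2. Unexpected SAEs traced through 9.2 to 9.4.**

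| Unexpected SAE | Class in 9.2 | 24 h, 'and' wording | 24 h, 'or' wording | 15-day REC report |
|---|---|---|---|---|
| Likely caused by the intervention | related | met | met | met |
| Likely caused by a research procedure | related only by elimination | met if 'the study' includes its procedures | met | not met as worded |
| Possibly related to the intervention, filed as related | related | met | met | met |
| Possibly related to the intervention, filed as unrelated | unrelated | not met | met | not met |

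Where the 24-hour rule is not met, the 14-day rule in 9.4 applies. The last two rows are the same event judged by two sites. The procedure row also has no fitting value in the SAE causality item, which asks about the intervention alone.

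**Step 3. The two 24-hour wordings.** They disagree on any unexpected SAE filed as unrelated. Under 'and' it goes by the 14-day route; under 'or' it is due within 24 hours. Both wordings stand in section 9.3.

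**Step 4. How much of the trial runs without the intervention.** The inputs are 80 participants, 1:1 randomisation, the intervention given on Day 0 in one arm and at the final visit in the other, and visits from day -28 to day 84. I assume 40 per arm, full follow-up and visits on the nominal day.

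- Days per participant: 28 + 84 = 112.
- Total participant-days: 80 × 112 = 8,960.
- Participant-days without the intervention: 40 × 28 + 40 × 112 = 1,120 + 4,480 = 5,600.
- Share: 5,600 / 8,960 = 62.5%.

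This is a share of observation time, not of events. It shows that the period in which only a procedure could be the study-related cause makes up most of the planned reporting period.

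**The case against.** The strongest reply is that 9.2 forces a choice, so every event receives a class, and that both descriptions open with 'e.g.' and may be illustrations rather than definitions. An event caused by a procedure cannot be *unrelated*, so *related* is the only class left. This is a fair reading and it narrows the gap in 9.2. It does not repair the REC trigger or the causality item in 9.3, which name the intervention alone and carry no 'e.g.'. It also gives a site no guidance on a possible relation.

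A reader might infer that SAEs caused by procedures escape the 24-hour sponsor report. The document does not support that: the phrase about relation to the study naturally includes its procedures, and the 'or' wording is broader still. A reader might also infer that some SAEs go unreported. They do not, because section 9.4 sends serious events outside the 24-hour rule to a 14-day report. Finally, a reader might infer that counts by relatedness in the safety results would be distorted. Section 11 promises only descriptive summaries of safety data and the synopsis only listings and summaries; neither specifies a breakdown by relatedness.

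Placing possible events under *related* is also a convention that 9.2 does not settle. What stands is that the text should settle it one way.

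**Conclusion.** The point holds as a minor one. Read literally, the 15-day REC trigger leaves out an unexpected SAE caused by a research procedure. A possibly related SAE can be filed either way at the four sites, with different reporting consequences. The 24-hour trigger is stated in two ways that cannot both apply.

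The size is small. Few related events are expected from a hand-held fan, breathing advice, spirometry, questionnaires and an inhaler sensor. COPD admissions, likely the most common serious events, are classed as expected. The consequence is delay or omission from the REC report and uneven handling between sites, not loss of events. No feasibility criterion or clinical outcome depends on it.

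The conclusion assumes that sites apply the wording of 9.2 and 9.3 as it stands. The AE report form is not shown, and its causality options may be wider or narrower than the Protocol text.

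**What to change.** 1. In 9.2, define *related* as possibly, probably or definitely related to the intervention or a research procedure, and *unrelated* as unlikely or definitely not related to either. If these are meant as definitions, drop the 'e.g.'.
2. In 9.3, name the intervention or a research procedure in the SAE causality item, the 24-hour sponsor trigger and the 15-day REC trigger.
3. In 9.3, reconcile the 'and' and 'or' wordings of the 24-hour trigger so that only one remains.
4. Check that the AE report form carries the same classes and wording.

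This is a cheap improvement: a few words in two sections and, if needed, one form field. The downside is possibly a few more expedited reports, because possible and procedure-caused events would now count as related.
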